## **1 INTRODUCTION**

## **1.1 Background**

Onychomycosis, a common pathology of the toenails, is even more prevalent among diabetic subjects. Nearly 26 million Americans suffer from diabetes, and approximately one-third of subjects with diabetes have toenail onychomycosis. Numerous studies have addressed the efficacy and safety of both topical and oral antifungal treatment options for onychomycosis in diabetic subjects. However, no study to date has specifically addressed the efficacy and safety of efinaconazole among diabetic subjects.

## **1.2 Potential Pharmacotherapy**

Despite the existence of numerous topical antifungal agents for onychomycosis, data investigating the efficacy of topical antifungal agents among exclusively diabetic patient cohorts is limited. Ciclopirox 8% was evaluated in 2007 as a topical solution among a cohort 49 diabetic subjects. The study witnessed clinical improvement in 63.4% of subjects, with 54.3% attaining mycologic cure (Brenner et al., 2007). An earlier, 2001 study of ciclopirox 8% solution summarized the results of a 215-person diabetic subset of subjects. This study was observational, noncomparative, and uncontrolled, thereby limiting the usefulness of the data. The study reported that the mean affected nail area decreased from 64.3% to 25.7% after 6 months of treatment (Seebacher, 2001).

## **1.3 Efinaconazole 10% Solution Description**

Efinaconazole 10% solution is a new triazole antifungal agent. The medication was developed specifically for the topical treatment of distal and lateral subungual onychomycosis (DLSO) (Gupta, 2014). The medication was developed with consideration of the existing triazole antifungals itraconazole and fluconazole, with the formulation developed to more effectively penetrate the nail plate. The preparation was further enhanced with the development of nail lacquers to avoid product build-up and to reduce removal time. The solution is, specifically, an inhibitor of sterol 14alpha-demethylase (14-DM) (Tatsumi, 2013). In broth dilution tests in vitro, the solution was found to be more potent against reference strains than other common antifungals, including terbinafine, ciclopirox, itraconazole, and amorolfine, (Jo Siu, 2013).

## **1.4 Efinaconazole Safety and Adverse Effects**

The safety of efinaconazole has been document in both Phase II and Phase III trials. Treatment associated adverse events have been relatively frequent by incidence, but of low morbidity and of frequency similar to vehicle alone. Two phase III studies noted rates for a single adverse event during treatment to be similar between efinaconazole to vehicle: in one study, 66% versus 61%, and in the second study, 64.5% versus 58.5% (Elewski, 2013). These adverse events included contact dermatitis (2.9% versus 1.9%, 1.4% versus 1.0%), eczema (3.4% versus 3.3%, information not available in the second study), application site dermatitis (3.5% versus 0.0%, information not available in the second study), and application site vesicles (2.0% versus 0.0%, information not available in the second study). Discontinuation of the study as a result of adverse events was low, with 3.2% of treatment versus 0.5% of vehicle in the first study and 1.9% versus 0.0% in the second.

An additional study investigated if efinaconazole had a relationship with contact sensitization (Del Rosso, 2013). The study involved nine applications of efinaconazole 10% solution versus

vehicle over a three week period, with multiple follow-up applications three weeks later. The study concluded that the cumulative irritation scores were comparable between efinaconazole and vehicle alone.

### ***1.5 Efinaconazole Indications***

It is currently indicated for onychomycosis of the toenails (s) due to:

- Trichophyton rubrum
- Trichophyton mentagrophytes

## **2 STUDY DESIGN**

### ***2.1 Study Objective***

The objective of this noncomparative, uncontrolled study is to determine the efficacy of topical efinaconazole 10% for toenail onychomycosis among subjects with diabetes mellitus. Specific indicators to measure efficacy of treatment will be the mycological cure rate, complete cure rate, and treatment success. Furthermore, an additional goal of the study is to gain knowledge of safety in the setting of a cohort of diabetic subjects. Safety will be determined by the incidence and nature of treatment associated adverse events. These will be recorded at each follow-up visit.

## **2.2 Treatment Groups**

Adult subjects (18 years or older) with a medical history of controlled type 2 diabetes mellitus will be considered for enrollment. Subjects will be eligible for enrollment if a clinical diagnosis of distal onychomycosis involving at least 20% of one great toenail (GT) has been made and confirmed by nail biopsy. There will be no restriction based on nail involvement; up to 100% of the nail may be involved. Furthermore, there will be no restriction based on toenail plate thickness. The enrollment period will be continued until 48 intention-to-treat subjects have been enrolled in the study.

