## **2.3 Study Duration**

The intended enrollment period will be six months, though this may be extended if necessary to achieve 48 intention-to-treat subjects. The treatment period, following enrollment, will be 50 weeks in duration. The intended total study duration, then, will be 76 weeks.

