## 4 SUBJECT SELECTION

Prior to enrollment, an informed consent must be obtained. Eligibility will be determined by the established inclusion and exclusion criteria. Assuming a 50% screen rate, it is anticipated that a total of 96 subjects will need to be screened to reach 48 intention-to-treat subjects. Using an estimate of 55% for mycologic cure, 48 subjects will yield a 95% confidence interval of 0.281.

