## **5.2 Follow-up Visits**

Subjects will be assessed at the screening, at baseline, and at every 10 weeks until week 50 (at weeks 10, 20, 30, 40, and 50). The final assessment (week 50) will include a complete history and physical examination, replacing the lower extremity focused physical examination.

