### ***6.3 Early Termination Appointment***

If the subject elects to discontinue the study prior to completion, the subject will be asked to attend an early termination appointment. This early termination appointment will replace the final office visit. It will include the procedures of a follow-up office visit, with the addition of a complete history and physical. Subjects will be provided increased, but not excessive, financial compensation as motivation for attending this appointment.

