## **7.1 Safety Evaluation**

Safety will be assessed by recording the nature, intensity, and duration of treatment related adverse events. Safety analyses will be performed on both an intention-to-treat and per-protocol analysis basis. The intention-to-treat population will include each patient receiving at least one dose of the medication, with at least one post-baseline assessment.

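### The 48 subjects called intention-to-treat must have a post-baseline assessment, so treated subjects who never return leave the cure-rate denominator and are in effect replaced

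*Combined protocol and SAP*

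**What the plan says.** Section 2.2 sets the recruitment stop: "The enrollment period will be continued until 48 intention-to-treat subjects have been enrolled in the study". Section 2.3 plans six months of enrolment, "though this may be extended if necessary to achieve 48 intention-to-treat subjects", followed by 50 weeks of treatment.

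The only definition of the set is in section 7.1: "The intention-to-treat population will include each patient receiving at least one dose of the medication, with at least one post-baseline assessment". Section 5.2 places the first scheduled follow-up visit at week 10. Section 6.3 asks subjects who choose to stop early to attend a termination appointment and says of it: "It will include the procedures of a follow-up office visit, with the addition of a complete history and physical". That appointment could fall before week 10.

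Section 4 gives the planning figures: "Assuming a 50% screen rate, it is anticipated that a total of 96 subjects will need to be screened to reach 48 intention-to-treat subjects". It then takes 55% mycological cure and 48 subjects and states a 95% confidence interval of 0.281. The primary endpoint in section 2.4.1 is the proportion with complete cure at week 50. No section defines a separate population for efficacy.

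**The concern.** A set that requires attendance after baseline is a modified intention-to-treat set, whatever it is called. Here the same post-baseline condition also decides who counts toward the recruitment target. A subject who takes the drug and is never seen again is left out of the 48, and enrolment runs on until another subject who did return makes up the number. No replacement rule is written, but sections 2.2, 2.3 and 7.1 together have that effect.

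The study is uncontrolled, so the proportion cured is the whole efficacy result and there is no comparator arm in which a similar exclusion might partly cancel. If the subjects who disappear are less often cured than those who return, the reported rate is too high for the treated population. Because the final count is always 48, a reader could not see from it how many were treated and lost.

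**Working it through.** **Inputs.** Target 48 and set definition (sections 2.2, 2.3, 7.1); 50% screen rate, 96 screened, 55% mycological cure, interval 0.281 (section 4). The share d of treated subjects with no post-baseline assessment is not in the documents; 5%, 10% and 15% are assumed.

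**1. The plan's own figures.**
- Screened: 48 / 0.50 = 96. This reproduces exactly, so 50% is the only factor applied.
- Interval: 2 × 1.96 × √(0.55 × 0.45 / 48) = 0.2815. The stated 0.281 is therefore a full width, and the half-width is 0.141.

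**2. When membership is known.** A subject joins the set at the first assessment after baseline. That is week 10 on schedule, earlier if a termination appointment is attended, or later if week 10 is missed and a subsequent visit is kept. The loss that matters is loss with no assessment at all after baseline.

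**3. Effect on the cure rate.** Count a never-assessed subject as not cured. Then

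rate in all treated = rate in the set × (1 − d)

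| d | Treated subjects needed for 48 in the set, 48/(1 − d) | Rate in all treated, 0.55 × (1 − d) | Difference from 55% | Relative inflation, 1/(1 − d) − 1 |
|---|---|---|---|---|
| 5% | 50.5 | 52.3% | 2.8 points | 5% |
| 10% | 53.3 | 49.5% | 5.5 points | 11% |
| 15% | 56.5 | 46.8% | 8.3 points | 18% |

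The relative inflation does not depend on the cure rate, so it applies equally to complete cure, the primary endpoint, for which the plan gives no expected rate.

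**4. Which rule produces the difference.** Take d = 10%. If enrolment stopped at 48 treated, the set would hold 48 × 0.90 = 43.2 subjects. If enrolment continues, it holds 48 of 53.3. The ratio of set to treated is 0.90 both ways, so the expected rate in the set is the same. The difference comes from the definition in 7.1. The stop rule restores the count to 48 and so conceals the loss.

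**5. Screening number, if the screen rate is the screening pass rate.** Screened = 48 / 0.50 / (1 − d) = 101.1, 106.7 and 112.9, that is 102, 107 and 113 rounded up. For 96 to suffice, the pass rate would have to be 0.50 / (1 − d) = 52.6%, 55.6% and 58.8%.

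**The case against.** Several stronger conclusions are tempting, and the documents do not support them.

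- *Membership is known only at week 10, and every earlier dropout is excluded.* Section 7.1 asks for any post-baseline assessment. The termination appointment in section 6.3, for which increased compensation is offered, can supply one before week 10, and a later visit can supply one afterwards. The affected group is narrower than all early dropouts. It is not empty by design: attendance at that appointment is only requested, and section 6.2 provides for subjects who cannot be located.
- *The study will fall short of 48.* It should not. Sections 2.2 and 2.3 keep enrolment open until 48 are reached, so the interval width of 0.281 at 55% also stands.
- *The 96 screened and the 76 weeks are errors.* Both are forecasts, and section 2.3 allows the enrolment period to be extended. The screen rate is not defined. Since section 4 applies it directly from screened to intention-to-treat subjects, it could be an overall yield that already includes early loss. That reading would rescue the 96, but not the denominator.
- *Replacement causes the bias.* It does not, as step 4 of the working shows.

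Two further objections carry weight. The definition sits in the safety section, and no passage says outright that it fixes the efficacy denominator. However, section 4 ties the 48 intention-to-treat subjects to cure-rate precision, and no alternative set is offered. Also, the loss may be small. Section 1.4 reports discontinuation for adverse events of 3.2% and 1.9% on efinaconazole in two phase III studies, and loss for that reason with no later assessment should be rarer still. Those figures do not cover subjects who stop attending for other reasons, so they do not settle d.

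**Conclusion.** The point holds in a limited form. Followed as written, the plan drops treated subjects with no post-baseline assessment from the 48, fills their places, and offers no other denominator for the cure rates. Relative to all treated subjects, the rate is biased upward by about 3 to 8 percentage points at the planning rate of 55%, against a half-width of 14 points. This is a moderate effect.

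The size rests on two assumptions: a loss of 5% to 15%, which the documents do not give, and counting never-assessed subjects as not cured. If such loss were zero there would be no effect; if those subjects were in truth cured as often as the rest there would be no bias. The plan gives no ground for relying on either. The missing allowance in the screening number is a secondary planning matter that depends on how the screen rate is read.

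**What to change.** In sections 2.2, 2.3, 4 and 7.1, state the target as 48 subjects enrolled and dispensed study drug at baseline, without replacement. Dispensing is a better anchor than first dose, because sections 5.1.6 and 5.3 have subjects apply the drug themselves and describe no observed application. Use all 48 as the denominator for the week-50 cure rates, and count a subject with no post-baseline assessment as not cured. A set that requires a post-baseline assessment can be reported as a secondary analysis, named modified intention-to-treat. Define the screen rate in section 4 as the proportion of screened subjects who are enrolled and dispensed drug. On that definition 96 × 0.50 = 48, and 26 + 50 = 76 weeks needs no wait for follow-up status.

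The cost is wording in four sections and no additional patients. The reported cure rate may be slightly lower, and fewer than 48 subjects may have observed follow-up data.

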## **2.3 Study Duration**

The intended enrollment period will be six months, though this may be extended if necessary to achieve 48 intention-to-treat subjects. The treatment period, following enrollment, will be 50 weeks in duration. The intended total study duration, then, will be 76 weeks.

## **2.4 Efficacy Endpoints**

Mycological cure will be defined as negative KOH examination and negative fungal culture of the target toenail sample.

Clinical cure will be defined as 0% clinical involvement of the target toenail. Almost clinical cure will be defined as  $\leq 10\%$  clinical involvement of the target toenail.

Complete cure will be defined as 0% clinical involvement and mycological cure. Treatment success will be defined as  $\leq 10\%$  clinical involvement of the target toenail and mycological cure.

### **2.4.1 Primary Endpoints**

1. The primary efficacy end point will be the proportion of subjects achieving complete cure at week 50.

### **2.4.2 Secondary Endpoints**

1. The secondary efficacy end points will include mycological cure rate, treatment success rate, clinical cure rate, and almost clinical cure rate.

### **2.4.3 Safety Endpoints**

1. Type of Adverse Events
2. Frequency of Adverse Events

## **2.5 Measurement Methods**

At each study visit, the treating podiatrist will visually and physically assess subjects.

## **3 POTENTIAL RISKS AND BENEFITS**

### **3.1 Adverse effects of Efinaconazole**

The following are documented adverse effects of efinaconazole 10% solution, from a large two-armed study (Elewski, 2013):

| N (%)  | Study 1                 |                   | Study 2                 |                   |
|--|-------------------------|-------------------|-------------------------|-------------------|
|  | Efinaconazole (N = 653) | Vehicle (N = 213) | Efinaconazole (N = 574) | Vehicle (N = 200) |
| No. of subjects who reported at least 1 TEAE                     | 431 (66.0%)             | 130 (61.0%)       | 370 (64.5%)             | 117 (58.5%)       |
| Individual TEAEs reported by >2% of subjects in at least 1 study |                         |                   |                         |                   |
| Application site dermatitis                                      | 23 (3.5%)               | 0 (0.0%)          | -                       | -                 |
| Application site vesicles  | 13 (2.0%)               | 0 (0.0%)          | 7 (1.2%)                | 0 (0.0%)          |
| Arthralgia   | 13 (2.0%)               | 7 (3.3%)          | 18 (3.1%)               | 2 (1.0%)          |
| Back pain  | 16 (2.5%)               | 6 (2.8%)          | 19 (3.3%)               | 7 (3.5%)          |
| Blood creatinine phosphokinase increased                         | -                       | -                 | 11 (1.9%)               | 5 (2.5%)          |
| Bronchitis   | 8 (1.2%)                | 4 (1.9%)          | 14 (2.4%)               | 3 (1.5%)          |
| Contact dermatitis   | 19 (2.9%)               | 4 (1.9%)          | 8 (1.4%)                | 2 (1.0%)          |
| Eczema   | 22 (3.4%)               | 7 (3.3%)          | -                       | -                 |
| Folliculitis   | 5 (0.8%)                | 5 (2.3%)          | -                       | -                 |
| Headache   | 15 (2.3%)               | 5 (2.3%)          | 25 (4.4%)               | 7 (3.5%)          |
| Hypertension   | 17 (2.6%)               | 10 (4.7%)         | 11 (1.9%)               | 5 (2.5%)          |
| Influenza  | 16 (2.5%)               | 8 (3.8%)          | 10 (1.7%)               | 1 (0.5%)          |
| Ingrowing nail   | 17 (2.6%)               | 1 (0.5%)          | 11 (1.9%)               | 2 (1.0%)          |
| Nasopharyngitis  | 78 (11.9%)              | 25 (11.7%)        | 63 (11.0%)              | 15 (7.5%)         |
| Procedural pain  | 10 (1.5%)               | 7 (3.3%)          | 6 (1.0%)                | 0 (0.0%)          |
| Sinusitis  | 30 (4.6%)               | 4 (1.9%)          | 17 (3.0%)               | 5 (2.5%)          |
| Tinea pedis  | 7 (1.1%)                | 6 (2.8%)          | 4 (0.7%)                | 6 (3.0%)          |
| Upper respiratory tract infection                                | 38 (5.8%)               | 13 (6.1%)         | 35 (6.1%)               | 11 (5.5%)         |
| Urinary tract infection  | 12 (1.8%)               | 8 (3.8%)          | 12 (2.1%)               | 2 (1.0%)          |

TEAE, Treatment-emergent adverse event.

Subjects will be advised to contact study coordinators if they notice signs of any of the aforementioned adverse effects.

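### The between-visit contact instruction in 3.1 is tied to a phase III list that names no foot ulcer, wound, soft-tissue infection or hospitalization, so such events could be reported up to 70 days late

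*Combined protocol and SAP*

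**What the plan says.** Section 3.1 presents adverse events from two phase III studies under the row label "Individual TEAEs reported by >2% of subjects in at least 1 study". Directly below the table it states: "Subjects will be advised to contact study coordinators if they notice signs of any of the aforementioned adverse effects". Section 5.3.2 places subject education in the consent process and cross-refers to 3.1 and section 4.

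On the population behind that table, section 1.1 says that "no study to date has specifically addressed the efficacy and safety of efinaconazole among diabetic subjects". Section 2.1 adds that "an additional goal of the study is to gain knowledge of safety in the setting of a cohort of diabetic subjects".

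Section 5.2 schedules assessments at screening, at baseline and then "at every 10 weeks until week 50 (at weeks 10, 20, 30, 40, and 50" weeks. At these visits the plan provides adverse-event monitoring (5.2.4), a lower-extremity examination at weeks 10 to 40 and a complete one at week 50 (5.2.2), and assessment by the treating podiatrist (2.5). The follow-up procedures in 5.2.3 include debridement of the target toenail.

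Section 7.2 defines an adverse event broadly, as an unintended clinical, imaging or laboratory finding associated with use of the treatment, whether or not causally related. Section 7.3 makes an event serious if, among other criteria, it requires hospitalization. Section 7.4 requires serious events to be reported within 24 hours of the study learning of them.

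**The concern.** The instruction borrows its scope from a table built for another purpose. A frequency cut-off selects common events, not important ones, and the source studies did not specifically address diabetic subjects. A subject who develops an open or infected area on a foot, or is admitted to hospital, finds no matching entry and so is not prompted to call before the next visit.

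Three things are at stake. The investigator may review the event weeks after onset. A serious event enters the 24-hour reporting process only once the study knows of it. And 7.1 asks for the nature, intensity and duration of events, which are less reliable when reconstructed from memory at a later visit. The safety endpoints in 2.4.3 are the type and frequency of adverse events, so complete and timely reports matter for the stated safety goal.

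**Working it through.** The plan gives no figure of its own for reporting delay. The check compares the scope of three sections and then takes the delay from the visit schedule.

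**Scope of the trigger (3.1).** The table has 19 event rows. They fall into three groups:
- *Local to skin or nail:* application site dermatitis, application site vesicles, contact dermatitis, eczema, folliculitis, ingrowing nail, tinea pedis.
- *General illness or symptoms:* arthralgia, back pain, bronchitis, headache, hypertension, influenza, nasopharyngitis, procedural pain, sinusitis, upper respiratory tract infection, urinary tract infection.
- *Laboratory only:* raised blood creatinine phosphokinase.

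The first group does contain foot and nail events: "Ingrowing nail", for example, was reported by 2.6% on efinaconazole against 0.5% on vehicle in Study 1, and by 1.9% against 1.0% in Study 2. Tinea pedis and folliculitis are superficial skin infections. No row names a foot ulcer, a wound, cellulitis or another soft-tissue infection, or a hospitalization.

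**What the cut-off can hide.** An event seen in 12 of 653 efinaconazole subjects in Study 1 (12/653 = 1.8%) and 11 of 574 in Study 2 (11/574 = 1.9%) would fall below 2% in both. If it was also below 2% on vehicle, 23 of 1,227 treated subjects could have had it and it would still be absent from the list, however serious it was. This shows how the filter works; it is not an estimate for any particular event.

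**Comparison with 7.2 and 7.3.** A new foot wound or infection could qualify as an adverse event under 7.2, and an admission to hospital meets 7.3. Neither is named by the trigger in 3.1. The subject-facing rule is therefore narrower than the rules the site must apply.

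**Size of the delay.**
- Input: visits at weeks 0 (baseline), 10, 20, 30, 40 and 50, from 5.2.
- Gaps between consecutive visits: 10, 10, 10, 10 and 10 weeks.
- Maximum delay to the next attended visit: 10 weeks × 7 = 70 days.
- Mean delay if onset is uniform between visits (an assumption): 10/2 = 5 weeks = 35 days.
- Maximum delay if one visit is missed: 2 × 10 = 20 weeks = 140 days.

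**What cannot be computed.** The documents give no rate for foot ulcer, wound or soft-tissue infection in this population, so the number of delayed reports among 48 subjects cannot be estimated. The rates in the 3.1 table do not help, because they describe events that the instruction already covers.

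**The case against.** A reader might infer four stronger things, none of which the documents support.

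- *Subjects are told to call only for listed effects.* The sentence contains no such restriction, and 5.3 promises that subjects' questions and concerns will be dealt with, although in the setting of self-administration. What stands is that the sentence prompts calls for listed effects and prompts none for others.
- *The list has no foot events.* It has several, as shown above. Moreover, the trigger is noticing signs of them, and redness or blistering could be taken as a sign of a listed dermatitis or vesicle. The gap is confined to ulcer, wound, soft-tissue infection and hospitalization.
- *The trial exists to find diabetic-foot events.* The objective in 2.1 is efficacy and the primary endpoint is "the proportion of subjects achieving complete cure at week 50". Safety in diabetic subjects is an additional goal, and no section names diabetic-foot events as a target.
- *Such events would be lost.* Each visit monitors for adverse events and examines the lower extremity, under a definition not limited to the table, and early leavers are asked to attend a termination appointment (6.3). Loss is conceivable only for a subject who stops attending and cannot be reached (6.2).

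Two further points count against the concern. Enrollment is limited to controlled type 2 diabetes (2.2), and peripheral arterial disease is an exclusion (4.3), which may make foot complications less frequent. And the consent pages are not in the text supplied; they may already carry broader contact wording, so its absence from the plan as a whole cannot be asserted. A 24-hour clock that runs from awareness is normal and is not itself a fault.

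None of this shortens the interval between visits or brings the sentence in 3.1 into line with 7.2 and 7.3.

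**Conclusion.** The point holds as a modest but worthwhile correction. The contact instruction in 3.1 is narrower than the plan's own definitions of adverse and serious adverse events. It omits the kinds of foot event that a safety goal in diabetic subjects would most want reported promptly, and it operates over five 70-day intervals. A subject following it as written could report such an event up to 70 days late, with a corresponding delay in investigator review and, for a serious event, in the 24-hour report.

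This rests on two assumptions: that visits are attended as scheduled, and that subjects receive no broader instruction through the consent form. For attending subjects the consequence is delay, not loss. No endpoint, sample size or efficacy analysis is affected.

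**What to change.** In 3.1, replace the closing reference to the effects listed above with: *any new or worsening symptom or health problem, whether or not listed above, including any skin break, wound or infection of a treated toe or foot, or any hospitalization*. Use the same wording in the subject education under 5.3.2. Check the consent form: if its contact instruction is already broader, align 3.1 with it so that subjects receive one message.

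The cost is one sentence, the matching education text, and a few more calls to coordinators. No visit, procedure, treatment or analysis changes.
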